1.1 Medical background

Atrial fibrillation (AF) is a cardiac rhythm disorder that can occur episodically or persistently. During AF, unco-ordinated electromechanical activity of the cardiac atria occurs, triggered by rapidly succeeding, disorderly impulses that can in some cases be transmitted to the cardiac ventricles. AF is the most common cardiac arrhythmia and is associated with considerable morbidity and mortality, due in particular to a 4- to 5-fold increase in the risk of thromboembolic strokes (1).

Due to the high thromboembolic risk in atrial fibrillation, it is a fundamental aim of treatment to reduce the secondary complications associated with atrial fibrillation and in particular the risk of stroke. Oral anticoagulation is usually recommended for this purpose (1;2). In Germany, phenprocoumon is most frequently used for anticoagulation with a vitamin K antagonist (VKA) (3).

In order to maintain the level of therapeutic anticoagulation within an optimum target range during treatment with VKA, the coagulation capacity of the blood must be closely monitored (i.e. at least every 3 – 4 weeks) by means of the INR value (4). This usually requires a visit to a physician, who can take a blood sample and perform the analysis (where necessary also via an external laboratory) and any dosage adjustment necessary.

The use of VKA is associated with various measures that can make it more difficult to use these drugs correctly. The narrow therapeutic window of VKA requires routine laboratory monitoring of coagulation (INR 2-3). However, optimal INR adjustment is often not obtained in everyday patient care in Germany either. The interactions of VKA with a number of medicines and foodstuffs require close monitoring and dosage adjustments following a change of concomitant medication or dietary habits. A recent analysis of German health insurance data came to the conclusion that AF patients with a moderate stroke risk and without any observable contraindication to OACs received no OAC on up to half the patient days observed (5).

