Dabigatran etexilate differs from VKA in that it does not intervene in the hepatic synthesis of coagulation factors, but indirectly competitively inhibits a specific plasma factor. Routine monitoring in the form of coagulation tests is required during therapy with VKA, as opposed to with the use of dabigatran etexilate, because the therapeutic margin of VKA is small and the anticoagulant effect can be affected by many interactions with other medicinal products, but also with certain foodstuffs (9, 10).

The pharmacodynamic effect of dabigatran sets in rapidly and also declines rapidly and therefore is easily controllable and predictable. That is an essential difference from the VKA, which only become effective after a few days if the concentration of vitamin K-dependent coagulation factors has declined sufficiently and only become ineffective after a few days if there is once again sufficient production of these factors in the liver.

2 Rationale, objectives and risk-benefit analysis

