4.1.3 Dosage

Treatment with dabigatran etexilate or VKA must be given in accordance with the data in the respective Summary of Product Characteristics and is based solely on medical therapeutic needs.

Pradaxa®

The recommended daily dose of Pradaxa® is 300 mg, taken in the form of one 150 mg capsule twice daily. Treatment should be long term.

For the following two patient groups, the recommended daily dose of Pradaxa® is 220 mg, taken as one 110 mg capsule twice daily:

- Patients \geq 80 years

- Patients receiving verapamil concomitantly.

For the following groups, a daily dose of 300 mg or 220 mg of Pradaxa® will be chosen on the basis of an individual assessment of the thromboembolic risk and the bleeding risk:

- Patients between 75 and 80 years old
- Patients with moderate renal impairment
- Patients with gastritis, oesophagitis or gastroesophageal reflux
- Other patients with an increased bleeding risk.

Note: The recommended doses in the Summary of Product Characteristics must not be exceeded.

VKA

VKA have no set dosage.

The dosage of VKA (e.g. phenprocoumon) must be monitored by determining the thromboplastin time and adapted individually. The outcome of this determination is given as INR (International Normalised Ratio).

The target is an effective range of 2.0–3.0 INR.

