5.2 Safety parameters**5.2.1 Safety endpoints**

In the context of this NIS, all emergent adverse events (S/AE) will be recorded approximately quarterly for 12 months in the eCRF.

In the event of treatment discontinuation, all emergent adverse events (S/AE) will be recorded in the eCRF up to 30 days after the end of treatment.

In the event of discontinuation of oral anticoagulation, the reasons for discontinuation and the subsequent antithrombotic stroke prophylaxis will be recorded.

5.2.2 *Investigation of adverse events*

5.2.2.1 *Definition of adverse events*

Adverse event:

Adverse events (AE) are all harmful, pathological or unintended changes of anatomical, physiological or metabolic functions, identifiable by physical signs, symptoms and/or changes in laboratory values that occur during the course of the NIS, irrespective of whether or not a relationship with a medication is assumed.

Regardless of whether a causal relationship exists with the consumption of the medication, adverse events include:

- all complaints by patients of a lack of well-being or subjective and objective symptoms (including clinically relevant changes in laboratory findings)
- new diseases and accidents observed during treatment with the medication
- the exacerbation of an existing disease
- the lack of efficacy of a medicinal product
- resistance formation
- abuse
- misuse
- overdose
- habituation, dependence
- off-label use
- interactions

Serious adverse event:

An adverse event is serious (SAE) if it

- results in death,
- is immediately life-threatening,
- results in permanent or significant disability/incapacity,
- requires or prolongs hospital treatment,
- involves congenital malformations or a birth defect,
- is otherwise medically significant.

Severity of an adverse event

The severity of adverse events must be documented in the (e)CRF and classified in accordance with the current version of the NCI-CTCAE criteria.

Causal relationship with an adverse event

The causal relationship must be medically assessed and evaluated and include all relevant factors, including the response pattern, time course, outcome after discontinuation of the trial medication or re-exposure, other confounding factors such as concomitant medication, concurrent diseases and relevant past history. The assessment of the causal relationship must be documented in the (e)CRF as follows:

Yes = There is a plausible causal relationship between the administered medication and the adverse event

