No = There is no plausible causal relationship between the administered medication and the adverse event

Exacerbation of pre-existing diseases and other pre-existing conditions

The exacerbation of pre-existing diseases and other pre-existing conditions is documented as an (S)AE in the (e)CRF.

Changes in vital signs, ECG, physical examination results and laboratory values

Changes in vital signs, ECG, physical examination results and laboratory values are documented as (S)AE in the (e)CRF if they are classed as clinically relevant by the observing physician.

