- Recording of the continuation of therapy with dabigatran etexilate (including dosage) or VKA since visit 3
- Onset of adverse events since visit 3
- Discontinuation of treatment with dabigatran etexilate or VKA since visit 3
 - Reasons for the discontinuation of treatment with dabigatran etexilate or VKA
 - Antithrombotic therapy after discontinuation of treatment with dabigatran etexilate or VKA
 - In the event of treatment discontinuation, all emergent adverse events (AE) are recorded in the eCRF up to 30 days after the end of therapy.

End of observation/Visit 5 (after about 12 months of use of dabigatran etexilate or VKA)

- Recording of the continuation of therapy with dabigatran etexilate (including dosage) or VKA since visit 4
- Onset of adverse events since visit 4
- Discontinuation of treatment with dabigatran etexilate or VKA since visit 4
 - Reasons for the discontinuation of treatment with dabigatran etexilate or VKA
 - Antithrombotic therapy after discontinuation of treatment with dabigatran etexilate or VKA
 - In the event of treatment discontinuation, all emergent adverse events (AE) are recorded in the eCRF up to 30 days after the end of therapy.
- Number of prescription-only medicines and daily intake

- Recording of disease severity (individual components of the CHA₂DS₂-VASc score) and bleeding risk (individual components of the HAS-BLED score)
- Recording of relevant comorbidities (Charlson et al. 1987)²¹

It is anticipated that anticoagulated patients will be invited for follow-up by the doctor at least quarterly. The quarterly recording of prescriptions and patient data therefore appears compatible with the real-life care situation in Germany.

7 Statistical analysis

All the analyses associated with this observational study are purely descriptive; results are to be interpreted exploratorily. There are no predefined confirmatory hypotheses and no measures are taken to maintain a study-wide 5% significance level or simultaneous confidence intervals.

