7.8 SAFETY ANALYSIS

The analysis of adverse events will be descriptive and conducted according to Boehringer Ingelheim standards. The main focus will be on treatment emergent events. All AE that occurred between start of treatment and six days after permanently discontinuation of therapy or end of study will be considered as treatment emergent and will be displayed in frequency tables for dabigatran etexilate and VKA treated patients, respectively. Non-treatment-emergent events will be assigned to “screening” or “post-treatment” and only be displayed in listings. All analyses will be based on the safety population.

Frequency, severity and causality of treatment-emergent AEs will be tabulated according to MedDRA-SOC and PT. Treatment-emergent SAEs will be tabulated as well as adverse events leading to treatment discontinuation.

Unless otherwise specified, the analyses of adverse events will be descriptive in nature. All analyses of AEs will be based on the number of patients with AEs and not on the number of AEs, except the analyses of action taken and the analysis of reason for serious TEAE.

An overall summary of adverse events will be presented.

The frequency of patients with adverse events will be summarised by treatment, primary system organ class and preferred term (mention MedDRA levels to be displayed in the tables). Separate tables will be provided for patients with serious adverse events. An additional table will be done for all non-serious adverse events with a frequency of more than 5%.

The system organ classes will be sorted alphabetically, preferred terms will be sorted by frequency (within system organ class).

For analysis multiple AE occurrence data on the CRF will be collapsed into an AE event provided that all of the following applies:

- All AE attributes are identical (PT, NCI grade, action taken, therapy required, seriousness, reason for seriousness, relationship, outcome)

Proprietary confidential information © 2015 Boehringer Ingelheim International GmbH or one or more of its affiliated companies

- The occurrences were time-overlapping or time-adjacent (time-adjacency of 2 occurrences is given if the second occurrence started on the same day or on the day after the end of the first occurrence). For classification into TEAE or Non-TEAE, the first documented start of event will be used.

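### INR-triggered adverse events can arise routinely only under VKA, and SAP 7.8 has no summary without them and no caveat on unequal testing

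*SAP*

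**What the plan says.** - **What counts as an AE.** The definition in Protocol 5.2.2.1 covers patient complaints, "including clinically relevant changes in laboratory findings". The recording rule in the same section reads: "Changes in vital signs, ECG, physical examination results and laboratory values are documented as (S)AE in the (e)CRF if they are classed as clinically relevant". That judgement is left to the physician. Neither text mentions INR.
- **Who is tested.** Protocol 1.2: "Routine monitoring in the form of coagulation tests is required during therapy with VKA, as opposed to with the use of dabigatran etexilate". Protocol 1.1 says that coagulation under VKA must be "closely monitored (i.e. at least every 3 – 4 weeks) by means of the INR value". Protocol 4.1.3 gives the reference: "The target is an effective range of 2.0–3.0 INR". Protocol 1.1 adds that "optimal INR adjustment is often not obtained in everyday patient care in Germany either". Protocol 2.3 limits procedures to usual care, so the study does nothing to even out testing.
- **What is tabulated.** SAP 7.8 states that treatment-emergent AEs "will be displayed in frequency tables for dabigatran etexilate and VKA treated patients, respectively". It plans an overall summary and tables by system organ class (SOC) and preferred term (PT), with severity and causality. The unit is the patient with an event. SAP 6.3 assigns safety to the Treated Set, which is not matched.
- **What is absent.** SAP 7.8 has no laboratory-only category, no summary without coagulation findings and no remark on unequal testing.

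**The concern.** An out-of-range INR without symptoms is found because the test is done. A comparable degree of over-anticoagulation under dabigatran would not routinely be detected, since no matching test is scheduled. The AE definition and collection window are the same for both drugs, but the chance of finding this class of event is not. Entries of this kind add to one column of a side-by-side table.

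At stake is how the AE summary is read. INR terms will have their own PT rows. Because the tables count patients, and one patient can appear in several rows, those rows cannot be subtracted exactly from the any-AE, related-AE, severity or SOC totals. Only someone with patient-level data can produce totals without them.

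**Working it through.** The plan gives no AE rate and no INR entry rate, so there is no figure to reproduce. What follows is an illustration.

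**Inputs from the documents.** Test interval of 3 to 4 weeks (Protocol 1.1). Twelve-month persistence *S* of 51%, 53.8% or 56.5% for VKA and 63% for dabigatran, with 800 patients per group (Local Amendment 1, change 3).

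**Assumptions, not in the documents.** Constant discontinuation hazard; a share *r* of INR tests that lead to an AE entry; a true any-AE proportion *p*; independence between tests and from other AEs. The six-day tail of the treatment-emergent window is ignored.

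**Step 1: tests per VKA patient.** Mean time on treatment in the year = (1 − S)/(−ln S). At 53.8% this is 0.462/0.620 = 0.745 years. Tests *n* = (52/4) × 0.745 = 9.7 to (52/3) × 0.745 = 12.9, or about 7,750 to 10,300 across 800 patients. Over 51% to 56.5%, mean time is 0.728 to 0.762 years and *n* is 9.5 to 13.2.

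**Step 2: upward contribution.** Share of VKA patients with at least one INR entry: q = 1 − (1 − r)^n. VKA any-AE proportion: 1 − (1 − p)(1 − q). At 53.8% persistence:

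| r | q | p = 20% | p = 30% | p = 50% |
|---|---|---|---|---|
| 0.1% | 1.0–1.3% | 20.8–21.0% | 30.7–30.9% | 50.5–50.6% |
| 0.5% | 4.7–6.3% | 23.8–25.0% | 33.3–34.4% | 52.4–53.1% |
| 1% | 9.3–12.2% | 27.4–29.7% | 36.5–38.5% | 54.6–56.1% |

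With p = 30%, the contribution is 0.7 to 0.9 points at r = 0.1% and 3.3 to 4.4 points at r = 0.5%.

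**Step 3: net difference between columns.** Step 2 uses the same *p* for both drugs. If the AE *hazard* is equal instead, shorter time on VKA lowers its proportion. With AE hazard λ and discontinuation hazard δ = −ln S, P(AE on treatment) = λ/(λ + δ) × [1 − exp(−(λ + δ))].

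- Setting dabigatran to 30% (S = 63%, δ = 0.462) gives λ = 0.459.
- The same λ gives VKA 27.5%, 28.1% and 28.7% at S = 51%, 53.8% and 56.5%.
- The INR share needed to bring VKA back to 30% is 1 − 0.70/(1 − VKA proportion): 3.5%, 2.7% and 1.9%.
- Through q = 1 − (1 − r)^n, that is r between about 0.14% and 0.37% of tests.
- At r = 0.1% the VKA column shows 28.2% to 29.6%, still below 30%. At r = 0.5% it shows 30.8% to 33.2%, above it.

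**The case against.** The strongest case against is that no passage says out-of-range INRs will be entered as AEs. The physician must first judge the change clinically relevant, and the protocol treats INR monitoring with dose adjustment as ordinary VKA care. Labile INR is also recorded separately as a HAS-BLED component. This stands as a limit on size: *r* is unknown and could be very small. It does not remove the asymmetry, because the judgement applies only where a test exists.

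Other points that stand in part:
- INR terms will appear on their own PT rows. It would be too strong to say that a reader cannot see or allow for them. The any-AE count without them lies between the published total and that total minus the INR-term counts. The exact figure is still out of reach.
- If INR problems cluster in certain patients, the same *r* affects fewer patients than Step 2 shows, since repeats in one patient count once.
- Safety is not a study objective, all analyses are descriptive, and the AE tables use an unmatched set. Removing INR entries would not make the columns comparable. Contact frequency may differ too: beyond INR checks, the protocol says only "It is anticipated that anticoagulated patients will be invited for follow-up by the doctor at least quarterly".
- A clinically relevant INR deviation can be a real drug effect. Taking such entries out of the main tables would risk understating VKA harm, so the all-inclusive tables should remain the main ones.

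**Conclusion.** The point holds as one about direction. INR-triggered entries add to the VKA column only, and the plan neither shows the totals without them nor warns of unequal testing. The contribution is about 1 percentage point at r = 0.1% and about 3 to 4 points at r = 0.5%. Those sizes rest on an assumed 30% base, constant hazards and independent tests, and on entry rates that the documents do not give.

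A reader might infer that the tables will show more harm under VKA even where clinical harm is identical, and so favour the sponsor's drug overall. The documents do not support that. Under the plan's own persistence figures and a 30% dabigatran proportion, equal hazards put VKA 1.3 to 2.5 points lower before any INR entry, so the net sign depends on the unknown entry rate.

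No objective, endpoint, error rate or sample size is affected. This is a cheap improvement to the safety reporting.

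**What to change.** In SAP 7.8:
1. Keep the all-inclusive AE tables as the main presentation.
2. Fix, before the analysis, a short list of MedDRA preferred terms for INR and prothrombin-time findings.
3. Add one supplementary by-drug summary (overall, SOC totals, related AEs, severity). In each row, leave out patients whose only qualifying entry is a term on that list.
4. State that coagulation laboratory events are routinely ascertained under VKA only, and that these rows are therefore not to be read as a drug comparison.

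Fixing the list in advance avoids a choice made after the counts are known. The cost is SAP wording and one extra set of tables, with no new data and no change at the sites.

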Reasons for change 2:

After 6 months of site and patient recruitment it became evident that the targeted patient and site numbers will not be met and that recruitment time should be longer.

Therefore the planned patient number will be reduced to 1600 and site number to 800.

Recruitment time will be prolonged to 16 months (LPI December 2015), thus study duration will also increase. LPO is now planned for December 2016.

Other timelines will change accordingly.

CHANGE 3: ADAPT TIME SCHEDULE, SITE NUMBERS AND PATIENT NUMBERS

Section of the protocol: Statistics Section Determination of number of patients

It is planned to include a total of 4000 patients in this non-interventional, controlled, observational study (dabigatran etexilate: 2000 patients, VKA: 2000 patients).

Calculation of statistical power:

All analyses are purely exploratory by virtue of the non-interventional study design. On the following assumptions:

- 15% drop-outs /missing values after one year,
- 2000 dabigatran etexilate patients, 2000 VKA patients, with 66% of VKA patients with a matching partner in the dabigatran etexilate group (i.e. total number of patients in the 1:1 matched analysis is 2640)
- a persistence rate of 63% in the dabigatran etexilate group (cf. 1-year persistence with a 60-day permissible medication gap as reported by Zalesak ¹⁹)).

the power for a descriptive p value ≤ 0.05 in a 2-tailed test for the same persistence rates is as follows (dependent on the VKA persistence rate):

Assumed VKA persistence rate*	51%	53.8%	56.5%
Power	100%	99.7%	91.7%

* The calculations were performed with ADDPLAN6 and are based on survival time analysis test statistics and the endpoint variables "Time to permanent treatment discontinuation".

Was changed to:

It is planned to include a total of 1600 patients in this non-interventional, controlled, observational study (dabigatran etexilate: 800 patients, VKA: 800 patients).

Calculation of statistical power:

All analyses are purely exploratory by virtue of the non-interventional study design. On the following assumptions:

- 15% drop-outs /missing values after one year,
- 800 dabigatran etexilate patients, 800 VKA patients, with 66% of VKA patients with a matching partner in the dabigatran etexilate group (i.e. total number of patients in the 1:1 matched analysis is 1056)
- a persistence rate of 63% in the dabigatran etexilate group (cf. 1-year persistence with a 60-day permissible medication gap as reported by Zalesak (¹⁹)).

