7. PLANNED ANALYSIS

All analyses in this study are descriptive; results are to be interpreted in an explorative manner.

For categorical variables summary tabulations of the number and percentage within each category (with a category for missing data) of the parameter will be presented. For continuous variables N, mean, SD, minimum, median, maximum and number of missing values will be presented. To achieve a valid comparability of compliance (persistence and adherence) patients prescribed to dabigatran etexilate or VKA will be matched 1:1 based on the Exposure Propensity Score (PS) and caliper matching with caliper of width equal to 0.2xStandard deviation of PS.

The Propensity Score will be calculated based on a logistic regression model taking the choice of treatment as dependent variable and baseline characteristics as independent variables into account. All baseline variables with an a priori association to persistence and adherence will be included into the regression analysis.

These variables correspond to the potential cofounder variables for a comparative analysis.

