7.7 EXTENT OF EXPOSURE

For duration of treatment see section 7.4. In addition, the duration of treatment with Viramune® will be given for the Treated Set with the number of patients and percentage in the following categories of duration:

<4 weeks, 4 - <10 weeks, 10-<30 weeks, 30-<50 weeks, 50-<70 weeks, ≥70 weeks.

In addition, the total treatment time of all patients will be provided in years.

Further on, the dosage of Pradaxa® at initial visit, which could be 2x110mg daily or 2x150mg daily, will be displayed (Section 7.1) as well as changes in dosage for the Treated Set.

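### Adverse-event tables show crude patient percentages by arm over a window that closes when treatment stops, with no rate per time at risk; if persistence differs as planned, the more persistent arm is expected to look slightly worse at equal event rates

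*SAP*

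**What the plan says.** SAP 7.8 sets the counting unit: "All analyses of AEs will be based on the number of patients with AEs and not on the number of AEs". The only exceptions are the analyses of action taken and of the reason for seriousness. The layout is by arm: "The frequency of patients with adverse events will be summarised by treatment, primary system organ class and preferred term". SAP 7 gives the general rule for categorical data: "For categorical variables summary tabulations of the number and percentage within each category".

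The time window comes from the same section. Events "between start of treatment and six days after permanently discontinuation of therapy or end of study will be considered as treatment emergent". For the rest: "Non-treatment-emergent events will be assigned to “screening” or “post-treatment” and only be displayed in listings". Protocol 7.3 has the same six-day rule.

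The primary endpoint (Protocol 5.1.1, SAP 5.1) is the time from initiation to permanent discontinuation. The event that ends the primary endpoint therefore also closes the adverse-event window, six days later.

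SAP 7.7 plans an exposure summary: "In addition, the total treatment time of all patients will be provided in years". It does not say that this total is split by arm or used with the adverse-event tables, and its sentence on duration of treatment names a product that is not a study drug. SAP Table 6.3: 1 assigns safety endpoints to the Treated Set, which is unmatched. Neither document writes down a rate per exposure time or a time-to-first-event estimate.

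**The concern.** A percentage of patients with at least one event rises with the time over which events are counted. Ending that time at discontinuation is an ordinary on-treatment convention and does little harm when arms are treated for similar periods. Here, whether treatment durations differ is the study's main question, and the power section assumes that they do: Local Amendment 1, Change 3 takes "a persistence rate of 63% in the dabigatran etexilate group" against 51%, 53.8% or 56.5% on VKA.

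If that assumption is right, patients in the two columns are observed for different lengths of time. A reader who compares the columns would see part of the persistence difference again, presented as a safety difference. A common 12-month window cannot replace the on-treatment window for everyone, because Protocol 5.2.2.2 ends event collection 30 days after premature discontinuation. A rate over time at risk is the natural alternative.

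**Working it through.** The documents give no expected adverse-event frequency, so there is no planned figure to reproduce on this point. The power table is used only as the source of the persistence and drop-out inputs.

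**Inputs from the documents (Local Amendment 1, Change 3).** 12-month persistence of 63% on dabigatran and 51%, 53.8% or 56.5% on VKA; 15% drop-out at one year; 800 patients per arm. Observation is about 12 months (Synopsis). The tail is 6 days (SAP 7.8).

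**Assumptions, not in the documents.** Constant stopping, drop-out and event hazards, independent of each other. The event rate *r* is the same in both arms, from 0.05 to 2 per patient-year. The planning persistence figures, set for the matched analysis, are applied to the Treated Set.

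**Step 1: mean time on treatment in the first year.** Stopping hazard λ = −ln(persistence); drop-out hazard μ = −ln(0.85) = 0.1625; k = λ + μ; mean = (1 − e^(−k))/k.

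| Persistence | λ | k | Mean (years) | 63% arm relative to this |
|---|---|---|---|---|
| 63% | 0.4620 | 0.6246 | 0.744 | – |
| 51% | 0.6733 | 0.8359 | 0.678 | 1.10 |
| 53.8% | 0.6199 | 0.7824 | 0.694 | 1.07 |
| 56.5% | 0.5709 | 0.7334 | 0.709 | 1.05 |

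With the six-day tail, the mean window is 8.99 months against 8.22, 8.41 and 8.58 months (ratios 1.09, 1.07, 1.05).

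**Step 2: expected crude percentage with at least one event.** The window is still open at time t with probability W(t) = exp(−λ·max(0, t − 6 days))·exp(−μt). The expected proportion is the integral from 0 to 1 year of W(t)·r·e^(−rt) dt.

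| r per year | Dabigatran 63% | VKA 51% | VKA 56.5% | Gap in points (51% / 56.5%) | Ratio (51% / 56.5%) |
|---|---|---|---|---|---|
| 0.05 | 3.66% | 3.35% | 3.50% | 0.31 / 0.17 | 1.093 / 1.047 |
| 0.5 | 30.25% | 27.89% | 29.00% | 2.36 / 1.25 | 1.084 / 1.043 |
| 1 | 49.80% | 46.28% | 47.94% | 3.52 / 1.86 | 1.076 / 1.039 |
| 2 | 71.21% | 67.11% | 69.04% | 4.10 / 2.17 | 1.061 / 1.031 |

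The 53.8% case lies between the two (28.46% at r = 0.5). The relative excess runs from about 3% to 9%.

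**Step 3: early-onset events.** If all risk falls in the first month, at a rate of 1 per year during that month and ignoring drop-out, the percentages are 7.90% and 7.86% (63% against 51% persistence). The gap is 0.04 points.

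**Step 4: sampling error.** At r = 0.5 with 800 per arm, the standard error of the difference is √(0.3025·0.6975/800 + 0.2789·0.7211/800) = 0.0227, or 2.3 points. The expected gap of 1.25 to 2.36 points is about one standard error or less.

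**Step 5: the same data as a rate.** Divide patients with a first event by time to first event or end of window. At r = 0.5 and 800 per arm, dabigatran gives 242.0 / 483.9 patient-years = 50.0 per 100. VKA at 51% persistence gives 223.1 / 446.2 = 50.0 per 100. Under these assumptions the rate removes the gap.

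**The case against.** The strongest reply is that the plan makes no safety comparison. The comparative objectives are persistence and adherence (Protocol 2.2), and the adverse-event analysis is descriptive, with no test, difference or ratio. The share of patients with an event while on drug is a valid description of just that. This stands, and it limits the point to how side-by-side figures will be read.

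Second, Protocol 7.3 and SAP 7.8 refer to sponsor standards that are not in the documents and might include rates. That cannot be excluded. The written SAP specifies patient counts only.

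Third, exposure is partly reported. SAP 7.4 gives persistence by arm, but for the matched cohort. SAP 7.7 gives a total, but does not say by arm. Neither supplies a denominator for the adverse-event tables.

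A reader might go further and infer any of three things that the documents do not support:

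- *That the plan builds in a bias against dabigatran.* The 63% and 51% to 56.5% figures are power assumptions for the matched analysis. Protocol 2.1 says that the question is unstudied in German care, and no persistence is assumed for the Treated Set. The direction depends on what is observed.
- *That the table of events leading to discontinuation is distorted in the same direction.* Those events themselves end treatment, so an arm with more of them also has lower persistence. The calculation above assumes independence and does not carry over.
- *That rates would license between-arm safety statements.* Protocol 7.1 expects the groups to differ because the doctor chooses treatment, and the Treated Set is unmatched. A rate corrects for time at risk only.

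**Conclusion.** The point holds as a modest defect of presentation. If persistence differs as the power section assumes and event hazards are constant and equal, the more persistent arm is expected to show a crude percentage about 3% to 9% higher in relative terms. That is 0.2 to 4.1 percentage points over assumed rates of 0.05 to 2 per patient-year, and almost nothing for events confined to the first weeks. In a single study, sampling error can mask or reverse it. The result rests on assumed event rates, on planning figures for persistence, and on stopping being independent of adverse events. It does not show that the safety results would mislead about either drug. It shows that the planned display lacks a common time base, although the dates needed to provide one are already collected.

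**What to change.** Keep the planned counts and percentages.

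- **SAP 7.8:** add, by arm, the number of patients with a first event per 100 patient-years at risk. Time at risk runs from start of treatment to the first such event or the end of the treatment-emergent window. Give this at least for the overall summary and for serious events and, where counts allow, by system organ class and preferred term.
- **SAP 7.7:** report total treatment time by arm for the study drugs, and correct the product name.
- **Accompanying note:** state that the rates are descriptive, come from the unmatched Treated Set, and remove neither confounding nor bias from stopping caused by adverse events.

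The cost is SAP wording and one extra column, with no new data. The downside is unstable rates for rare terms, which is why the finer breakdown should depend on counts.
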